Sodium Citrate 4% Locking Solution for Children Requiring Home Parenteral Nutrition

NCT04756427

January 25, 2022

JHM IRB - eForm A – Protocol

- Use the section headings to write the JHM IRB eForm A, inserting the appropriate material in each. If a section is not applicable, leave heading in and insert N/A.
- When submitting JHM IRB eForm A (new or revised), enter the date submitted to the field at the top of JHM IRB eForm A.

1. Abstract

Children with intestinal failure require long-term central venous catheters for home parenteral nutrition and are at high risk for central line-associated blood stream infections (CLABSI). Ethanol 70% locks are no longer available to use as prophylaxis as recent manufacturer price changes have made them cost-prohibitive for home health companies, and ethanol is not compatible with all tunneled catheters used for home parenteral nutrition. Another FDA-approved product does not exist; therefore, the standard of care is to use heparin locks, which prevent thrombus but have no antimicrobial activity. Sodium citrate 4% has been safe and effective for use in children with dialysis catheters, which are very similar to the central catheters used for home parenteral lines for children requiring home parenteral nutrition. Reducing the risk of CLABSI with have a significant impact on the health and quality of life of our pediatric patients. Children with CLABSI require intravenous antibiotic treatment and frequent hospitalization, which includes risk of septic shock and death. Frequent hospitalization negatively impacts the quality of life for both the child with intestinal failure and their family.

2. **Objectives** (include all primary and secondary objectives)

Our objectives are 1) to determine if the safety of sodium citrate prophylaxis 4% locks is different from the standard of care using heparin locks in children with central lines for long-term home parenteral nutrition, and 2) to determine the efficacy of sodium citrate 4% locks in preventing central line-associated blood stream infections in children with central lines for long-term home parenteral nutrition.

3. Background (briefly describe pre-clinical and clinical data, current experience with procedures, drug or device, and any other relevant information to justify the research)

Among our pediatric intestinal failure population on home parenteral nutrition, our CLABSI rate ranges from 4-7 infections/1,000 line days, which is similar to other sites.(1, 2) Our current standard of care is to use daily heparin locks in the central line for anti-coagulation, and if recurrent CLABSI occurs, we previously used 70% ethanol locks 3 days per week as a means of infection prophylaxis. However, there are several problems with ethanol: 1) ethanol is not compatible with polyurethane catheters, which are occasionally used in our population 2) manufacturing has recently changed and this product is now cost prohibitive and no longer available to most of our home care companies, and 3) our CLABSI rate has not noticeably improved with its use.

There is not another FDA approved infection prophylaxis lock available in the US. Other products are available in Canada and Europe, including sodium citrate. Through quality improvement initiatives, some centers have transitioned from heparin to sodium citrate 4% locks as standard of care for dialysis catheters.(3, 4) A recent international evidence based review also recommended citrate as a locking solution for non-hemodialysis catheters.(5)

Potential Benefits. Sodium citrate has both anti-coagulant and anti-microbial activity and is indicated for use a sa daily lock. The antimicrobial/anti-biofilm properties are likely related to citrate's chelation of ions, such as calcium, which destabilizes bacterial cell walls, whereas heparin may actually facilitate biofilm formation.(6) Sodium citrate (4%) is FDA approved for

hemodialysis and apheresis catheters, and it has been used in both adults and children. Similar to our indwelling catheters, hemodialysis catheters are also made of both silicon and polyurethane, and sodium citrate is not contraindicated with either material. Sodium citrate is also compatible with antibiotic locks that are commonly used to help treat CLABSI when it does occur.(7, 8)

Sodium citrate locks – 3 ml syringes of locking solution will be prepared by the infusion pharmacy using commercially available 4% sodium citrate IV fluid (available in 500 ml bags). The sodium citrate locks will be instilled into the central catheter daily during the period that parenteral nutrition is not infusing, and will be withdrawn and disposed of prior to resuming infusion of parenteral nutrition. If subjects are hospitalized, sodium citrate locks will be temporarily held during the duration of the inpatient stay, and will be resumed once the subject is discharged home.

Metrics - The primary outcome will be CLABSI rate, defined as a positive central line culture in the absence of other known primary infection per 1,000 line days. Secondary outcomes will be frequency of central catheter thrombus, any serious adverse event (hospitalization for any reason or death), or catheter removal per 1,000 line days. Other variables – Demographics, age, underlying gastrointestinal disorder, comorbidities, catheter type, and catheter insertion date will also be recorded

b. If your study involves data/biospecimens from participants enrolled under other research studies with a written consent or under a waiver of consent, please list the IRB application numbers for those studies. Please note: Certificate of Confidentiality (CoC) protections applied to the data in source studies funded by NIH or CDC will extend to this new study if the funding was active in 2016. If this situation applies, Section 36, question 4 in the application will need to be answered "Yes" and "Hopkins Faculty" should be selected in question 7. No other documents are required.

Our intestinal failure patients are also enrolled in our prospective database IRB00077416 with overlapping clinical data which can be used for comparison to historical adverse events, including CLABSI.

c. Study duration and number of study visits required of research participants.

The study period will be twelve month. Subject will continue their routine monthly outpatient visits, as well as urgent visits for fever.

d. Blinding, including justification for blinding or not blinding the trial, if applicable. Not applicable e. Justification of why participants will not receive routine care or will have current therapy stopped.

Routine care with heparin provides insufficient CLABSI prophylaxis. No other therapy will be changed.

- f. Justification for inclusion of a placebo or non-treatment group. Not applicable
- g. Definition of treatment failure or participant removal criteria. Significant adverse event due to sodium citrate 4%, such as recurrent central line thrombus, significant bleeding, significant electrolyte instability not due to other etiologies, or cardiac arrythmia
- h. Description of what happens to participants receiving therapy when study ends or if a participant's participation in the study ends prematurely.

If the subject withdraws from the study, they will resume standard of care heparin locks. Once the study is completed, if there have been no adverse events due to sodium citrate 4%, we propose continuing to use sodium citrate 4% as the daily locking solution.

5. Inclusion/Exclusion Criteria

Inclusion criteria - Pediatric patients (<22 years) requiring long-term (>3 months) home parenteral nutrition who have had at least one central line-associated blood stream infection. Parenteral nutrition must be cycled to 22 hours or less (>2 hours per day where parenteral nutrition is not infusing).

Exclusion criteria – patients with known cardiac arrhythmias, hypersensitivity to citrate, pregnancy, or receiving continuous parenteral nutrition (infusing over 24 hours).

6. Drugs/ Substances/ Devices

- a. The rationale for choosing the drug and dose or for choosing the device to be used. See background. This drug and dose has been safe and effective when used in similar dialysis catheters
- b. Justification and safety information if FDA approved drugs will be administered for non-FDA approved indications or if doses or routes of administration or participant populations are changed.

The drug is FDA approved for similar dialysis catheters.

c. Justification and safety information if non-FDA approved drugs without an IND will be administered.

7. Study Statistics

a. Primary outcome variable.

The primary outcome will be CLABSI rate, defined as a positive central line culture in the absence of other known primary infection per 1,000 line days.

 b. Secondary outcome variables.
 Secondary outcomes will be frequency of central catheter thrombus, any serious adverse event (hospitalization for any reason or death), or catheter removal per 1,000 line days

c. Statistical plan including sample size justification and interim data analysis. A predetermined sample size will not be used. All eligible, consented subjects will be enrolled. The frequency and proportion of adverse events will be compared to our historical control population of home parenteral nutrition subjects who used either heparin or ethanol locks, who are already enrolled in a prospective observational cohort to monitor outcomes (IRB00077416) using descriptive statistics

d. Early stopping rules. Based on the safety of previous studie

Based on the safety of previous studies, we do not anticipate the need for early stopping. Given our small population, adverse events will be monitored quarterly. If there is a significant change in frequency of events that appear to be directly related to sodium citrate 4%, the study will be stopped early.

8. Risks

- a. Medical risks, listing all procedures, their major and minor risks and expected frequency. Please see the Background for additional information. Bleeding risk is low and similar to heparin. At high concentration, other risks have been reported: sodium citrate 12% has been associated with protein precipitate, and sodium 46% has been associated with hypocalcemia and arrhythmia
- b. Steps taken to minimize the risks. To minimize risk, we are using the previously well tolerated 4% sodium citrate solution. The lock withdrawn and discarded after dwelling in the catheter to prevent systemic circulation. If the sodium citrate enters systemic circulation, the most likely outcome is metabolism to bicarbonate.
- c. Plan for reporting unanticipated problems or study deviations. The data will be monitored quarterly and unanticipated problems or deviations will be reported to the IRB
- d. Legal risks such as the risks that would be associated with breach of confidentiality. We do not anticipate greater risk of breach of confidentiality by participation in this study. Only minimal data is recorded, and it is stored in a secure, HIPAA compliant online database, only accessible by study members.
- e. Financial risks to the participants.
 There will be no direct costs to the subjects. We will request insurance coverage of the sodium citrate locks to be included in the per diem parenteral nutrition charge, similar to the way heparin locks are already included as standard of care. Clinic visits and laboratory tests are scheduled as standard of care. If insurance declines to cover the cost of the locks, we will not enroll the subject in the study.

9. Benefits

a. Description of the probable benefits for the participant and for society.

Subjects may directly benefit from study participation by reducing risk of CLABSI. Determining if sodium citrate is safe and effective will benefit the vulnerable intestinal failure population in general.

10. Payment and Remuneration

a. Detail compensation for participants including possible total compensation, proposed bonus, and any proposed reductions or penalties for not completing the protocol. Subjects will not be compensated financially for participating in the study.

11. Costs

a. Detail costs of study procedure(s) or drug (s) or substance(s) to participants and identify who will pay for them.

Sodium citrate locks can be compounded and shipped out by the Johns Hopkins pharmacy in a 14-day supply. The cost of a 14-day supply of sodium citrate locks is \$182 (\$7/day x 14 days for drug, \$34 for compounding session, \$50 delivery fee). The cost of 1 year of participation would be \$4,732 (\$182 x 26 weeks) per subject. We will request insurance coverage for the cost. If we are unable to get insurance coverage, the subject will not be enrolled.

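### The all-cause SAE outcome includes CLABSI admissions and no non-CLABSI admission rate is planned, so it cannot separate the CLABSI benefit from a change in other admissions.

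*Combined protocol and SAP*

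**What the plan says.** Section 2 sets as the first objective "to determine if the safety of sodium citrate prophylaxis 4% locks is different from the standard of care using heparin locks". Sections 4a (Metrics) and 7b list the same secondary outcomes: catheter thrombus, then "any serious adverse event (hospitalization for any reason or death), or catheter removal per 1,000 line days". The primary outcome in both sections is the CLABSI rate per 1,000 line days.

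The Abstract links the two: "Children with CLABSI require intravenous antibiotic treatment and frequent hospitalization". Section 3 gives the local background: "our CLABSI rate ranges from 4-7 infections/1,000 line days".

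The analysis in section 7c is descriptive: "The frequency and proportion of adverse events will be compared to our historical control population". The controls come from an existing database which, according to section 4b, has "overlapping clinical data which can be used for comparison to historical adverse events, including CLABSI". Sections 4a and 4b thus both place CLABSI among the adverse events.

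No section plans an admission rate by cause, or one with CLABSI admissions removed.

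**The concern.** A CLABSI that leads to admission is counted twice: once in the efficacy outcome and once in the SAE outcome. If citrate works as hoped, the all-cause SAE rate falls through that route alone. A reader of the safety table then cannot tell three situations apart: fewer CLABSI admissions with nothing else changed, fewer admissions of every kind, and fewer CLABSI admissions partly or wholly offset by more admissions for other reasons. The third is the one a safety objective most needs to expose.

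Subtracting the reported CLABSI rate from the SAE rate is not a reliable repair. The documents do not say that each CLABSI corresponds to exactly one admission.

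**Working it through.** The plan states no admission rate or effect size, so there is no figure of its own to reproduce. The check asks how far the all-cause ratio can depart from the ratio for other admissions.

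**Inputs from the documents.** CLABSI rate 4 to 7 per 1,000 line days (section 3), taken as 4, 5.5 and 7. Accrual of 10–15 children a year for 3–5 years with 12 months of follow-up each (section 4a) gives 10 × 3 = 30 to 15 × 5 = 75 child-years.

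**Assumed inputs.** Share of CLABSIs admitted: 0.5 or 1. Other admissions, *o*: 0.5, 1 or 2 per child-year. Ratio for CLABSI, *c*: 0.5 or 0.75. Ratio for other admissions, *k*: 1, 1.5 or 2. One child-year is 365 line days, and deaths are ignored. This gives 3 × 2 × 3 = 18 settings for each pair (*c*, *k*).

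**Formulas.** CLABSI admissions per child-year: *m* = rate × 0.365 × share admitted. All-cause ratio = (*c·m* + *k·o*) / (*m* + *o*).

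| CLABSI ratio | Other admissions | All-cause ratio | Settings at or below 1.00 |
|---|---|---|---|
| 0.5 | unchanged | 0.58–0.87 | 18 of 18 |
| 0.5 | × 1.5 | 0.66–1.23 | 13 of 18 (2 near-ties at 0.999) |
| 0.5 | × 2 | 0.75–1.60 | 7 of 18 (2 near-ties at 0.999) |
| 0.75 | unchanged | 0.79–0.93 | 18 of 18 |
| 0.75 | × 2 | 0.95–1.67 | 2 of 18 (1 near-tie) |

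**What the split adds.** Take the mid setting: 5.5 per 1,000, all admitted, *o* = 1, *c* = 0.5. Then *m* = 5.5 × 0.365 = 2.0075. Cohorts of equal size are assumed, with Poisson counts and exact conditional 95% intervals.

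- Other admissions doubled. All-cause: (1.004 + 2) / (2.0075 + 1) = 3.004 / 3.008. At 30 child-years this is 90 v 90, ratio 1.00 (0.74–1.35). Non-CLABSI: 60 v 30, ratio 2.00 (1.27–3.21). At 75 child-years: 1.00 (0.82–1.20) against 2.00 (1.51–2.68).
- Other admissions × 1.5. All-cause: (1.004 + 1.5) / 3.008 = 0.83. Non-CLABSI at 30 child-years: 45 v 30, ratio 1.50 (0.92–2.47). At 75 child-years: about 1.5 (1.10–2.03).
- Repeat admissions in one child widen these. With variance twice Poisson, the doubling at 30 child-years is exp(ln 2 ± 1.96 × √(2 × (1/60 + 1/30))) = 1.08–3.72. By the same formula the × 1.5 rise at 75 child-years is about 0.99–2.27.

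The doubling example is chosen at a break-even point. A CLABSI reduction fully offsets a rise of *m*(1 − *c*)/*o*, here 2.0075 × 0.5 / 1 = 1.00, which is exactly a doubling. Elsewhere the masking is partial.

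**Misclassification.** If a share *q* of CLABSI admissions is missed and counted as non-CLABSI, the ratio reads (*k·o* + *q·c·m*) / (*o* + *q·m*). For *k* = 2: (2 + 0.100) / (1 + 0.201) = 1.75 at *q* = 0.1, and 1.57 at *q* = 0.2. For *k* = 1: 0.92 and 0.86. The all-cause ratios in the same two cases are 1.00 and 2.004 / 3.008 = 0.67.

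**The case against.** The strongest reply is that the protocol itself counts CLABSI as an adverse event, so a fall in CLABSI admissions is a safety gain on the plan's own terms. That stands. A reader might infer that any fall in the SAE rate would be an artefact, and the documents do not support that. What remains is that the all-cause rate mixes this gain with everything else.

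Second, the all-cause rate is not the only safety information. Thrombus, catheter removal and CLABSI are separate outcomes, and section 7c compares adverse events generally. The stopping rule (7d) and removal criteria (4g) turn on events attributed to citrate, not on the SAE ratio. This also stands: it would go too far to say that Objective 1 has no usable outcome, or that a stopping or removal decision rests on the diluted rate. None of these items supplies the non-CLABSI admission rate, however.

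Third, the split is imperfect. It cannot resolve a 50% rise at 30 child-years, it misclassifies some stays, and culture-negative fever admissions would fall on the non-CLABSI side. A reader might expect it to settle the safety question. It does not; it makes the comparison interpretable.

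Fourth, section 7c's controls used heparin or ethanol while Objective 1 names heparin, and section 5 requires a prior CLABSI of subjects while no such condition is stated for controls. Splitting admissions cures neither limit, and the intervals above do not reflect them.

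**Conclusion.** The point holds as a matter of interpretation. The SAE outcome contains the efficacy event, no non-CLABSI admission rate is planned, and a CLABSI benefit can therefore mask a rise in other admissions. That the all-cause ratio is pulled down follows from the definition; by how much rests on the assumed share admitted and the assumed rate of other admissions.

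If CLABSI is halved, masking of a 50% rise is common across the settings (13 of 18) and masking of a doubling less so (7 of 18). With a 25% reduction, full masking of a doubling is rare (2 of 18). These figures show what the outcome could hide, not what is likely. Section 3 reports 4% citrate as well tolerated in dialysis and apheresis catheters, and nothing in the documents suggests that other admissions will rise.

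All-cause hospitalization or death is a legitimate outcome and should stay. The plan should be amended, but the study is not invalid without the change.

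**What to change.** In sections 4a and 7b, keep all-cause hospitalization or death. Add two secondary outcomes, CLABSI hospitalizations and non-CLABSI hospitalizations, each per 1,000 line days and each in both cohorts.

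Classify admissions by one date rule, fixed before the data are compared and identical in both cohorts: an admission is CLABSI-related if the culture for a CLABSI counted in the primary outcome falls within a stated window around the admission date. Close the window early in the stay, so that a CLABSI arising late in an admission for another reason does not relabel that admission. Record the reason for admission for new subjects, and show culture-negative fever admissions as a sub-row where the reason is known.

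The cost is protocol wording, a few table rows and one supporting field. Much of the data should already be at hand for the citrate cohort: both events are needed for the planned rates, and section 4a requires the site to know about inpatient stays ("If subjects are hospitalized, sodium citrate locks will be temporarily held during the duration of the inpatient stay").

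There are two downsides. Some stays will be misclassified in either direction, and attribution is unblinded, which is why the all-cause outcome stays and the date rule takes precedence over the recorded reason. Historical admission dates may also be missing for some controls; if they are, only the citrate cohort's split rates can be reported, and the report should say so.

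### Section 7c plans only a descriptive comparison with historical controls; it should state a CLABSI rate ratio per line day with a 95% CI clustered on the child.

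*Combined protocol and SAP*

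**What the plan says.** Section 2 sets two comparative aims: "to determine if the safety of sodium citrate prophylaxis 4% locks is different from the standard of care using heparin locks" and "to determine the efficacy of sodium citrate 4% locks in preventing central line-associated blood stream infections".

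Sections 7a and 7b put the outcomes on an exposure scale. The primary outcome is the "CLABSI rate, defined as a positive central line culture in the absence of other known primary infection per 1,000 line days". The secondary outcomes are "frequency of central catheter thrombus, any serious adverse event (hospitalization for any reason or death), or catheter removal per 1,000 line days".

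Section 7c then gives the whole statistical plan. On size: "A predetermined sample size will not be used". On analysis: "The frequency and proportion of adverse events will be compared to our historical control population". The controls are home parenteral nutrition patients on heparin or ethanol locks, "who are already enrolled in a prospective observational cohort to monitor outcomes (IRB00077416) using descriptive statistics". Sections 4a and 4b both count CLABSI among adverse events, so this sentence also governs the primary outcome. Whichever part of the sentence the closing words about descriptive statistics belong to, no other method is named anywhere.

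Section 4b adds that the clinic's intestinal failure patients are also in the database that supplies the controls.

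**The concern.** To determine efficacy, or whether safety differs, one must compare two groups and say how precise the comparison is. Section 7c names no contrast (ratio or difference), no interval and no model. With no predetermined sample size, an interval would be the only statement of precision, and none is planned. Two rates printed side by side would leave the reader unable to tell a real reduction in CLABSI from chance in a few dozen children.

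Three smaller gaps follow from the first.

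- **Repeat events.** Section 3 itself mentions recurrent CLABSI, but nothing says how several events in one child are handled.
- **Children in both groups.** Because of the shared database, one child may contribute time to both groups.
- **Heparin.** The first objective names heparin, while 7c describes a control population on heparin or ethanol and plans no comparison with heparin alone.

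**Working it through.** The protocol states no power, effect size or interval, so there is no figure to reproduce. The check asks what its own inputs imply.

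**Inputs from the protocol.** Background rate 4-7 CLABSIs per 1,000 line days (Section 3). Enrolment of 10-15 a year for 3-5 years, and 12 months' follow-up (Section 4a).

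**Assumptions, not in the protocol.** 365 line days per child; a control group of equal size and exposure; independent groups unless stated; between-child variation in risk ranging from none (Poisson) to a gamma distribution with shape k = 2 or k = 1, where 1/k is the between-child variance and 1/k = 0 is Poisson.

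**1. Events**
- Children: 10 × 3 = 30 to 15 × 5 = 75.
- Line days: 30 × 365 = 10,950 to 75 × 365 = 27,375.
- CLABSIs per child-year: m = 4 × 365/1,000 = 1.46 to 7 × 365/1,000 = 2.56.
- Total with no citrate effect: 30 × 1.46 = 43.8 to 27,375 × 7/1,000 = 191.6.
- Share of children with two or more, even at identical risk: 1 − e^(−m)(1 + m) = 43% to 72%.

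**2. Chance alone, true ratio 1**

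var(log ratio) = 2/(nm) + 2/(nk); 95% range = exp(±1.96 × √var).

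| Setting | Variation | Variance | 95% range |
|---|---|---|---|
| n = 30, 4/1,000 | Poisson | 2/43.8 = 0.0457 | 0.66-1.52 |
| n = 30, 4/1,000 | k = 1 | 0.0457 + 2/30 = 0.1123 | 0.52-1.93 |
| n = 75, 7/1,000 | Poisson | 2/191.6 = 0.0104 | 0.82-1.22 |
| n = 75, 7/1,000 | k = 1 | 0.0104 + 2/75 = 0.0371 | 0.69-1.46 |

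A much larger control group does not remove this. With unlimited controls the variance halves, and 30 citrate children at 4/1,000 still give 0.74-1.34 (Poisson) to 0.63-1.59 (k = 1).

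**3. Why any interval should be clustered on the child**

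Between-child variation inflates the variance of the event count by 1 + m/k, which is 1.73 (m = 1.46, k = 2) to 3.56 (m = 2.56, k = 1). A nominal 95% interval that treats events as independent then excludes a true ratio of 1 with probability 2[1 − Φ(1.96/√(1 + m/k))] = 13.6% to 29.9%. Simulation (20,000 runs per setting, k = 1-2) agrees: 13-30% ignoring the child, 5.4-7.0% clustered, and 5.1-6.2% clustered with a small-sample correction. With no between-child variation all are about 5-6%, so clustering costs little if it proves unnecessary.

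If half the children were in both groups but were coded as different children, the interval would be too wide (error 2.0-3.8%). One identifier across both groups gives 4.9-5.5%.

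**4. Would the interval be informative?**

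Take a true ratio of 0.5, so that citrate events are half of control events; var = 1/control events + 1/citrate events + 2/(nk).
- n = 30, 4/1,000: 1/43.8 + 1/21.9 = 0.0685, giving 0.30-0.84 (Poisson). Adding 2/30 = 0.0667 for k = 1 gives 0.24-1.03.
- n = 75, 7/1,000: 1/191.6 + 1/95.8 = 0.0157, giving 0.39-0.64. Adding 2/75 = 0.0267 for k = 1 gives 0.33-0.75.

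The interval is wide at the low end of enrolment and useful at the high end.

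**The case against.** **This is an observational cohort with no fixed sample size, and an interval could be added at analysis.** That is true if the database holds line days and a child identifier. It limits the harm, but the plan still does not commit to an interval. Observational rates can be compared with a ratio and interval without a hypothesis test or power calculation.

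**The magnitudes rest on assumptions.** This stands. Control numbers, between-child variation, overlap and the ratio of 0.5 are not in the protocol. The whole-clinic rate is also applied to children selected for a prior CLABSI, whose rate may be higher. The gap in 7c itself is read directly from the text and needs none of these figures.

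**The 13-30% error is not a consequence of 7c.** Correct: 7c plans no interval. The figure shows only why an interval, once added, should allow for the child.

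**The wrong scale.** A reader might infer that 7c abandons the line-day rate. Sections 7a and 7b already fix that scale, so what is missing is the contrast and its precision.

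**A stronger reading on bias.** Citrate subjects must be patients "who have had at least one central line-associated blood stream infection", and 7c sets no such condition for controls. A reader might infer that the comparison is biased against citrate. The protocol does not support a direction. Section 3 says ethanol was used after recurrent CLABSI, so ethanol controls may have had more prior infections than citrate subjects. In the same gamma model (k = 1-2, look-back of 1 or 3 years, no true effect), unselected controls give a ratio of 1.04-1.41. Ethanol controls, taken as having at least two prior CLABSIs, give 0.78-0.95, and a half-and-half mix gives 0.98-1.00. Neither the heparin/ethanol mix nor the look-back is stated. For the same reason, a fixed control window starting at a first CLABSI is not clearly an improvement: with look-backs of 12 months in one group and 36 in the other, the ratio could still be 0.84-1.19 with no true effect.

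**Conclusion.** The point holds as one about precision and repeat events. The comparison in 7c cannot by itself meet the aims in Section 2, because it gives no effect measure and no statement of chance error. The gap should be fixed before the analysis.

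Its practical size, as an illustration only: at the low end of enrolment an apparent one-third reduction (ratio 0.66) lies at the edge of what chance alone produces when all children share one risk, and well inside it when risks vary strongly. At the high end the chance range narrows to 0.82-1.22 (Poisson) or 0.69-1.46 (k = 1). These ranges assume equal, independent groups, full 12-month follow-up and the clinic's overall CLABSI rate.

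Selection of the historical controls is a real limitation, but its size and direction cannot be determined from the protocol. It should be reported as a limitation and not as a known bias.

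**What to change.** In Section 7c, state:

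> The primary comparison is the CLABSI rate per 1,000 line days in each group, and the rate ratio (citrate vs historical control) with a 95% CI clustered on one child identifier spanning both groups (for example a log-linear model with a log line-days offset, robust standard errors and a small-sample correction, or a bootstrap by child). Secondary outcomes are compared in the same way, as events per 1,000 line days. The comparison with heparin-lock time, which the first objective names, is also reported on its own. Proportions are supportive only.

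Add one sentence naming, as a limitation, that citrate subjects are selected on a prior CLABSI and that the controls' CLABSI history and heparin/ethanol mix may differ from theirs.

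**Cost.** One paragraph and modest analysis time. The control database must be checked for line days and for an identifier that links to study subjects. Intervals may be wide at low enrolment, and wider for heparin time alone if that leaves few control events. The interval describes chance error only, not confounding from historical controls. Treatment, visits and enrolment do not change.
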